6.14.4 VFQ-25 Questionnaire Evaluation

Scores from the VFQ-25 questionnaire determined at the first and month 12 visits will be compared separately in the “Approved treatment regimen” and “Wait and extend” treatment regimen groups using the Wilcoxon Signed Rank Test.

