2.2 Secondary objectives

- to compare mean change in CRT at 12th month from baseline between two groups with OCT
- to assess the number of injections needed over a 12-month treatment period with a “wait and extend” dosing regimen
- to assess the number of visits needed over a 12-month treatment period with a “wait and extend” dosing regimen
- to evaluate the number of patients with improvement in BCVA from baseline
- to evaluate the number of patients with improvement of 5 or more letters from baseline
- to evaluate the number of patients with improvement of 10 or more letters from baseline
- to evaluate the number of patients with improvement of 15 or more letters from baseline
- to evaluate the safety of intravitreal injections of Lucentis (ranibizumab) in patients with DME
- to describe the change in Patient reported functional ability of Lucentis-treated patients.

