6.6.2 Health-related Quality of Life

Visual Function Questionnaire – 25 (VFQ – 25), will be completed at the selected sites at visits Baseline/Visit 2, and 12. month. VFQ-25, is a questionnaire consists of 25 questions aiming to evaluate the general visual function of the patients. VFQ-25 will be applied by the

investigator. VFQ-25 scores will be calculated according to the related guidelines. (Mangione et al. 1998, 2001).

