9.5 Analysis of secondary variables

9.5.1 Efficacy variables

- Mean change in CRT (μm) by Optical coherence tomography at 12th month from baseline
- Mean no. of injections over a 12-month treatment period
- Mean no. of visits over a 12-month treatment period
- Proportion of patients who gained ≥ 0 , ≥ 5 , ≥ 10 and ≥ 15 letters in BCVA at 12th month
- Incidence of adverse events (AEs) and serious AEs (SAEs), by ophthalmic examinations and IOP measurements, and by changes in vital signs and laboratory parameters over the 12-month assessment period.
- Mean change in VFQ25 scores at 12th month from baseline

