9.5.4 Health-related Quality of Life

Quality of Life variables will include the total score and sub-scores of the Visual Function Questionnaire – 25 (VFQ – 25) Descriptive statistics will be given including the changes according to the baseline.

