3.2. SECONDARY OBJECTIVES

- To compare the mean change in CRT from baseline at month 12 between the two groups using OCT
- To evaluate the number of injections required for a treatment period of 12 months with a “wait and extend” dosing regimen
- To evaluate the number of visits required for a treatment period of 12 months with a “wait and extend” dosing regimen
- To evaluate the number of patients with improvement in BCVA from baseline
- To evaluate the number of patients with improvement of 5 or more letters from baseline
- To evaluate the number of patients with improvement of 10 or more letters from baseline
- To evaluate the number of patients with improvement of 15 or more letters from baseline
- To evaluate the safety of intravitreal Lucentis (ranibizumab) injections in patients with DME
- To describe patient-reported change in functional ability in patients treated with Lucentis

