6.14.2 Optical Coherence Tomography

The mean change from baseline to month 12 in Central Retinal Thickness determined with Optical Coherence Tomography for both eyes will be calculated for both groups and will be compared using the Mann Whitney u test.

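### SAP 6.14.4 adds within-arm VFQ-25 tests to a descriptive protocol plan and gives no between-arm estimate, so the regimens cannot be compared on this outcome

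*SAP*

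**What the plan says.** The SAP has one VFQ-25 analysis, in section 6.14.4: "Scores from the VFQ-25 questionnaire determined at the first and month 12 visits will be compared separately in the" labeled-regimen and wait-and-extend "treatment regimen groups using the Wilcoxon Signed Rank Test". It names no between-arm test, difference or confidence interval, and no summary of change.

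The protocol is more modest. Its objective (section 2.2) is "to describe the change in Patient reported functional ability of Lucentis-treated patients", and SAP 3.2 matches it: "To describe patient-reported change in functional ability in patients treated with Lucentis". Protocol 9.5.4 asks for summaries only: "Descriptive statistics will be given including the changes according to the baseline". The outcome is nevertheless an efficacy variable, listed in the synopsis and in Protocol 9.5.1 as "Mean change in VFQ25 scores at 12th month from baseline".

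Other efficacy outcomes are compared between arms. For retinal thickness, SAP 6.14.2 says mean change "will be calculated for both groups and will be compared using the Mann Whitney u test". SAP 6.14.1 compares the letter-gain proportions between arms by chi-square or Fisher's exact test.

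On collection, Protocol 6.6.2 says the questionnaire "will be completed at the selected sites at visits Baseline/Visit 2, and 12. month". Note i to the visit schedule (Protocol section 6) allows it at either of the first two visits. The SAP refers to the first visit.

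**The concern.** A signed-rank test within an arm asks whether scores moved between baseline and month 12 in that arm. It cannot separate the regimen's effect from a time trend, regression to the mean or a general effect of being treated. Randomisation deals with those through the contrast between arms, and for VFQ-25 that contrast is not planned.

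Two p-values printed next to each other are easily read as a comparison: significant in one arm, not in the other, therefore different. That inference is invalid, and it can arise often when the arms are the same. VFQ-25 is the only patient-reported outcome in the trial. The report would contain two tests, but no estimate of how far the regimens differ in patient-reported function and no statement of how uncertain that difference is.

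**Working it through.** **The plan's own figure.** No effect size, SD, alpha or number of patients is given for VFQ-25. The only sample size is for the primary BCVA comparison: 43 per arm, margin 5 letters, SD 7, significance level 0.025, 90% power (Protocol 9.7, SAP 5.1). Taking the level as one-sided and the true difference as zero, n = 2 × (7/5)² × (1.960 + 1.282)² = 41.2, so 42 per arm. The noncentral t calculation gives 89.9% power at 42 and 90.6% at 43, so 43 is reproduced. It serves below as a reference size for VFQ-25.

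**Inputs for the check.**
- Number per arm: 43 as reference. 20 is an assumption for participation by selected sites only; 52 is the number per arm to be included (Protocol 9.7).
- Alpha: two-sided 0.05 for each within-arm test (assumption).
- True change: 0 to 0.8 SD of the change score, the same in both arms (assumption).

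**Formula.** With equal arms and within-arm power a, P(exactly one arm significant) = 2a(1-a). It peaks at 50% when a = 0.5. It is 32% at a = 0.2 or 0.8, 18% at a = 0.9 and 9.5% at a = 0.05.

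**Simulation.** 20,000 runs, normal change scores, a signed-rank test in each arm, 43 per arm:

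| True change in both arms (SD) | Within-arm power a | 2a(1-a) | Simulated split results |
|---|---|---|---|
| 0 | 0.047 | 0.090 | 8.9% |
| 0.2 | 0.237 | 0.362 | 36% |
| 0.3 | 0.461 | 0.497 | 50% |
| 0.4 | 0.706 | 0.415 | 41% |
| 0.5 | 0.881 | 0.210 | 21% |
| 0.6 | 0.964 | 0.069 | 7% |
| 0.8 | 0.999 | 0.002 | 0.2% |

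The number per arm shifts the peak without removing it. At 20 per arm, split results occur in 36% of runs at 0.3 SD, 50% at 0.5 SD and 16% at 0.8 SD. At 52 per arm the figures are 50% at 0.3 SD, 12% at 0.5 SD and 3% at 0.6 SD.

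**The direct comparison.** One Mann-Whitney test of change between the same equal arms rejects in 4.5% to 5.2% of runs at every effect size and number tried.

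**Precision of a between-arm estimate.** The unadjusted 95% CI half-width in SD units of change is t(0.975, 2n-2) × √(2/n). At 43 per arm this is 1.989 × 0.2157 = 0.43 SD. It is 0.64 SD at 20 per arm and 0.39 SD at 52.

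**The case against.** The strongest reply is that nothing promised is missing. Both documents word the objective as describing change in treated patients. The retinal thickness objective, by contrast, says to compare the groups, and it gets a between-arm test. A reader might infer that the SAP fails a comparative VFQ-25 objective; there is no such objective. This part of the reply stands.

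Secondly, a signed-rank test in each arm is a legitimate answer to whether scores changed there, and SAP 6.14.4 does not say that the two p-values will be set against each other or used to rank the regimens. That also stands: the harm comes from a reading that the plan invites but does not itself make.

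Thirdly, the risk figures rest on assumptions and are high only in the middle of the range. A reader might infer that a split result is likely whatever the data. The table does not support that: the chance is about 9% with no change and below 10% again from 0.6 SD upward at 43 per arm.

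Fourthly, the SAP does not withdraw the protocol's descriptive summaries. If they are reported by arm, a reader could derive an unadjusted difference. The between-arm estimate would also be imprecise, has no margin to be judged against, and comes from an open-label study in which the investigator applies the questionnaire (Protocol 5.4, 6.6.2). These are reasons to label it supportive. They do not favour two within-arm p-values, which have the same limitations and hide the imprecision.

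**Conclusion.** The point holds as a minor one. SAP 6.14.4 goes beyond the protocol's descriptive plan by adding within-arm tests, and it leaves a listed efficacy variable of a randomised trial without any between-arm estimate. The tests are valid for change within an arm and uninformative about the difference between regimens.

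If the p-values are nevertheless compared, truly equal arms give a split result in anything from 0.2% to 50% of trials at 43 per arm. The peak lies near 0.3 SD, where within-arm power is close to one half. This range depends on the assumed alpha, effect size and number per arm. The absence of any estimate of the difference does not depend on them. The primary analysis and the sample size are unaffected.

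**What to change.** In SAP 6.14.4:

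1. Report mean VFQ-25 change from baseline to month 12 in each arm with a 95% CI. This meets the stated objective and Protocol 9.5.4.
2. Replace the within-arm p-values with the between-arm difference in change, adjusted for baseline VFQ-25 score (for example by ANCOVA), with a 95% CI.
3. Label that difference as supportive, since VFQ-25 has no margin and no power calculation and the study is open-label. State the number of patients per arm who contribute, because only selected sites take part.
4. As a minor alignment, define the baseline score as the one taken at Visit 1 or Visit 2, following note i of the visit schedule. The SAP's reference to the first visit, read literally, could leave out scores taken at Visit 2.

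The cost is SAP wording and one extra estimate from data already collected. There is no change to conduct or sample size.

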6.15 SAFETY ASSESSMENT

6.15.1 Adverse / Serious Adverse Events

The list of the Adverse / Serious Adverse Events (SAE) reported in each visit will be provided. All adverse events will be examined regarding the visits they occurred, severity (mild, moderate, severe), relationship with the drug (suspected, not suspected), outcome (continuing, resolved), actions taken (no action taken, dose adjusted/dosing interrupted, additional treatment given, non-pharmacological treatment given, hospitalized), additional treatments if applicable, time between hospitalization and discharge dates, and length of hospital stay.

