FFA	Fundus fluorescein angiography
FSH	Follicle-stimulating hormone
HA	Health Authority
IEC	Independent Ethics Committee
logMAR	Logarithm of the minimum angle of resolution
MedDRA	Medical dictionary for regulatory activities
OCT	Ocular coherence tomography
RPE	Retinal pigment epithelium
SAE	Serious Adverse Event
SBP	Systolic blood pressure
SD	Standard deviation
SOP	Standard Operating Procedure
VA	Visual acuity
VEGF	Vascular endothelial growth factor
VFQ-25	Visual Function Questionnaire
WOCBP	Women of childbearing potential

Glossary of terms

Assessment	A procedure used to generate data required by the study
Enrollment	Point/time of patient entry into the study; the point at which informed consent must be obtained (i.e. prior to starting any of the procedures described in the protocol)
Investigational drug	The drug whose properties are being tested in the study; this definition is consistent with US CFR 21 Section 312.3 and is synonymous with “investigational new drug” or “investigational medicinal product.”
Investigational treatment	All investigational drug(s) whose properties are being tested in the study as well as their associated treatment controls. This includes any placebos, any active controls, as well as approved drugs used outside of their indication/approved dosage or tested in a fixed combination. Investigational treatment generally does not include other treatments administered as concomitant background therapy required or allowed by the protocol when used within approved indication/dosage
Medication number	A unique identifier on the label of each investigational/study drug package in studies that dispense medication using an IRT system
Subject Number	A number assigned to each patient who enrolls into the study
Premature patient withdrawal	Point/time when the patient exits from the study prior to the planned completion of all investigational/study treatment administration and all assessments (including follow-up)
Randomization number	A unique identifier assigned to each randomized patient, corresponding to a specific treatment arm assignment
Stop study participation	Point/time at which the patient came in for a final evaluation visit or when study/investigational treatment was discontinued whichever is later
Study drug/ treatment	Any single drug or combination of drugs administered to the patient as part of the required study procedures; includes investigational drug (s), active drug run-ins or background therapy

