5.5.8 Prohibited Treatment

Any concomitant medications including prescription drugs or over-the-counter preparations used by a patient during the study and until the conclusion of the study participation (except for routine medications given for ocular procedures required by the protocol, i.e. fluorescein, dilating drops, topical antibiotic, topical anesthetic) must be recorded on the Concomitant medications/Significant non-drug therapies CRF including start and stop dates and reason for use.

Laser photocoagulation for DME is permitted only as rescue treatment according to predefined criteria and needs to be

recorded on the Concomitant medications/Significant non-drug therapies CRF

Use of the following treatments is NOT allowed after the start of the study:

- Chronic concomitant therapy with topical ocular corticosteroids
- Other intravitreal medication in the study eye
- Systemic medications known to be toxic to the lens, retina or optic nerve, including Deferoxamine, Chloroquine/ hydroxychloroquine (Plaquenil), Tamoxifen, Phenothiazines and Ethambutol
- Treatment with glitazones during the study.
- Any other investigational drug

The below treatments will be prohibited 30 days before randomisation: verteporfin (Visudyne®), external beam radiation treatment, , submacular surgery or other surgical interventions for DME.

The below treatments will be prohibited 90 days before randomisation: focal laser photocoagulation treatment.

The below treatments will be prohibited 120 days before randomisation: macular laser photocoagulation treatment.

During the study, below treatment will be permitted: Retrobulber anesthesia to prevent eye movements, metochloropamide or other treatments for preventing the nausea due to fluorescein injection and other routine treatments for glaucoma. The patient will also be provided an additional topical antimicrobial medication to use 3 days after the injection which will be used 4 times a day.

If the investigator decided that the other eye (other than the study eye) has a DME lesion or has a new DME lesion occurred during the study which needs treatment, appropriate routine ranibizumab treatment will be applied by the investigator; however any data will not be collected for the other eye. The ranibizumab treatment applied to the other eye will be given by NOVARTIS.

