7.1 Adverse events

An adverse event (AE) is any untoward medical occurrence (i.e., any unfavorable and unintended sign [including abnormal laboratory findings], symptom or disease) in a subject or clinical investigation subject *after providing written informed consent* for participation in the study. Therefore, an AE may or may not be temporally or causally associated with the use of a medicinal (investigational) product.

The occurrence of adverse events should be sought by non-directive questioning of the patient at each visit during the study. Adverse events also may be detected when they are volunteered by the patient during or between visits or through physical examination, laboratory test, or other assessments.

Abnormal laboratory values or test results constitute adverse events only if they fulfill at least one of the following criteria:

- they induce clinical signs or symptoms,
- they are considered clinically significant,
- they require therapy.

Clinically significant abnormal laboratory values or test results should be identified through a review of values outside of normal ranges/clinically notable ranges, significant changes from baseline or the previous visit, or values which are considered to be non-typical in patient with underlying disease. Investigators have the responsibility for managing the safety of individual patient and identifying adverse events. Alert ranges for labs and other test abnormalities are included in Appendix 1.

Adverse events should be recorded in the Adverse Events CRF under the signs, symptoms or diagnosis associated with them accompanied by the following information.

- the CTCAE grade

If CTCAE grading does not exist for an adverse event, use 1=mild, 2=moderate, 3=severe, and 4=life-threatening. CTCAE Grade 5 (death) is not used, but is collected in other CRFs (Study Completion, Death/Survival).

- its relationship to the study treatment (no/yes)
- its duration (start and end dates) or if the event is ongoing an outcome of not recovered/not resolved should be reported.
- whether it constitutes a serious adverse event (SAE)
- action taken regarding study treatment
- whether other medication or therapies have been taken (concomitant medication/non-drug therapy)
- its outcome (not recovered/not resolved; recovered/resolved; recovering/resolving, recovered/resolved with sequelae; fatal; or unknown)

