7.2 Serious adverse event reporting

To ensure patient safety, every SAE, regardless of causality, occurring after the patient has provided informed consent and until 30 days after the last study visit must be reported to Novartis within 24 hours of learning of its occurrence.

Any SAEs experienced after the 30 days period should only be reported to Novartis if the investigator suspects a causal relationship to study treatment.

Recurrent episodes, complications, or progression of the initial SAE must be reported as follow-up to the original episode, regardless of when the event occurs. This report must be submitted within 24 hours of the investigator receiving the follow-up information. An SAE that is considered completely unrelated to a previously reported one should be reported separately as a new event.

Information about all SAEs is collected and recorded on the paper Serious Adverse Event Report Form. The investigator must assess the relationship to study drug, complete the SAE Report Form in English, and send the completed, signed form by fax within 24 hours to the local Novartis Drug Safety and Epidemiology Department. The telephone and telefax number of the contact persons in the local department of Novartis Drug Safety are listed in the investigator folder provided to each site and is also listed below. The original copy of the SAE Report Form and the fax confirmation sheet must be kept with the case report form documentation at the study site. Follow-up information should be provided using a new paper SAE Report Form stating that this is a follow-up to a previously reported SAE and sent by giving the original report date.

Follow-up information provided should describe whether the event has resolved or continues, if and how it was treated, whether the treatment code was broken or not and whether the patient continued or withdrew from study participation. Each re-occurrence, complication, or progression of the original event should be reported as a follow-up to that event regardless of when it occurs.

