9.5.2 Safety variables

All safety evaluations will be summarized and submitted for each visit per treatment arm.

All adverse events will be summarized per treatment arm, as patient numbers and per cents for any adverse event experience and adverse events for each system organ class will be summarized. All information collected (i.e.: severity or grade or causality assessment) will be summarized. Deaths and SAEs requiring early discontinuation will be summarized separately.

Laboratory details will be submitted as the descriptive statistics of the core data and for changes in the baseline data for each treatment arm (mean, median, standard deviation, interval) will be analyzed by highlighting the clinically notable changes.

Vital signs will be summarized and descriptive statistics will be given for heart rate and pulse in a sitting posture including the baseline changes.

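### SAP 6.15.1 drops adverse-event outcome and severity levels that the protocol collects, and plans no by-arm summary of study-eye or injection-procedure events

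*SAP*

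**What the plan says.** **Outcome and severity.** Protocol 7.1 records for each event "its outcome (not recovered/not resolved; recovered/resolved; recovering/resolving, recovered/resolved with sequelae; fatal; or unknown", together with the CTCAE grade. Where CTCAE has no grading, it uses a scale from 1 (mild) to 4 (life-threatening). CTCAE Grade 5 is not used, and death is captured on other CRF pages. SAP 6.15.1 classifies the same events as mild, moderate or severe, and by "relationship with the drug (suspected, not suspected), outcome (continuing, resolved".

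**Arm.** Protocol 9.5.2 summarises all adverse events per treatment arm as patient numbers and percentages, and says that "adverse events for each system organ class will be summarized". It also summarises the collected grade and causality information, and treats deaths separately. SAP 6.15.1 promises a list by visit and an examination of event attributes. It mentions neither arms nor percentages.

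**Causality.** Protocol 7.1 asks for "its relationship to the study treatment (no/yes". The protocol glossary defines study drug/treatment as "Any single drug or combination of drugs administered to the patient as part of the required study procedures". For serious events, Protocol 7.2 says "The investigator must assess the relationship to study drug". SAP 6.15.1 also names only the drug.

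**Eye.** The adverse-event items listed in Protocol 7.1 and SAP 6.15.1 do not include the affected eye. Protocol 5.5.8 says that, if the fellow eye needs treatment for DME, "appropriate routine ranibizumab treatment will be applied by the investigator". The same sentence adds that data on that eye will not be gathered.

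**The concern.** The title promises a comparison of safety as well as efficacy, and a secondary objective in Protocol 2.2 is the safety of the intravitreal injections. Both arms receive ranibizumab 0.5 mg. What the regimens can change is how often, and when, the study eye is injected. Harm from the injection procedure in the study eye is therefore a natural safety contrast, and the adverse-event plan has no table for it.

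Two things are at stake. First, an ocular event that leaves permanent damage is the outcome a reader would most want to see, yet the SAP has no category for it. Labelled resolved, it looks benign. Labelled continuing, it looks like any open event. Second, an investigator who follows the glossary can properly mark a needle-related event as not related to the drug. In the causality output it then sits with events that have nothing to do with treatment.

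**Working it through.** The plan states no adverse-event rate and no power for safety, so there is no figure of its own to reproduce on this point. The check is a comparison of the texts.

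**1. Outcome.** Each Protocol 7.1 outcome is placed in the SAP 6.15.1 list:

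| Protocol 7.1 | SAP 6.15.1 |
|---|---|
| not recovered | continuing |
| recovering | continuing (a judgement) |
| recovered | resolved |
| recovered with sequelae | no category |
| fatal | no category |
| unknown | no category |

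Six levels are collected and two are reported. Three of the six have no place: "recovered/resolved with sequelae; fatal; or unknown".

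**2. Severity.** The protocol's fallback scale has four levels and the SAP has three: 4 − 3 = 1 level missing, life-threatening. The same gap applies to CTCAE Grade 4.

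**3. Arm.** Protocol 9.5.2 requires a summary by arm. SAP 6.15.1 does not mention one, although other SAP sections do state both treatment groups (for example 6.7 on ECG and 6.13 on concomitant medication).

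**4. Causality.** The adverse-event item, the serious-event form and the SAP all refer to the study treatment or the drug. None has a separate item for the injection procedure.

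**5. Eye.** Both eyes are examined at every visit (Protocol 6.6), and Protocol 7.1 counts any untoward occurrence in the patient. Read with those sections, the fellow-eye sentence in Protocol 5.5.8 leaves two possibilities. If fellow-eye events are recorded, no planned adverse-event table separates them from study-eye events. If they are not, adverse-event capture is incomplete. The documents do not say which applies.

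**6. Denominator.** Protocol 9.5.1 lists the mean number of injections without restricting it to one arm. SAP 6.14.3 names only wait and extend, so the SAP plans no per-injection rate for both arms.

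**7. What by-arm tables could show.** This is an illustration with assumed patient-level event risks, because the documents give none. Arm sizes are the 43 and 52 of Protocol 9.7, and the test is two-sided at 0.05. With p̄ the mean of the two risks:

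power = Φ{[|p1 − p2| − 1.96·√(2p̄(1 − p̄)/n)] / √(p1(1 − p1)/n + p2(1 − p2)/n)}

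For 20% against 10% with n = 52: (0.100 − 1.96 × 0.0700)/0.0693 = −0.537, so power is about 30%.

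| Assumed risks | n = 43 per arm | n = 52 per arm |
|---|---|---|
| 10% v 5% | 14% | 16% |
| 20% v 10% | 25% | 30% |
| 40% v 20% | 53% | 61% |

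The safety tables will therefore be mainly descriptive. The exact categories shown matter more than any test on them.

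**The case against.** The strongest reply is that little is really lost. Events are MedDRA-coded (Protocol 8.3) and summarised per arm by system organ class (Protocol 9.5.2). A randomised comparison of recognisable procedure-type events needs no causality rating, and marking an event as unrelated does not remove it from those tables. Other planned data also bear on injection harm: pressure before and 60 minutes after injection (Protocol 6.6), right- and left-eye examination tables (SAP 6.8.1), the study eye itself (SAP 6.2) and a symptom call after each injection (notes to the Protocol section 6 schedule). This stands, and it rules out several stronger readings that a reader might infer:

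- *That injection harm cannot be compared.* Incidence by arm and term can be. What is missing is a planned summary by eye and by relation to the procedure.
- *That eyes are pooled.* No section says so. The documents are silent on the affected eye, and Protocol 5.5.8 says fellow-eye data are not gathered. The CRF is not among the documents, so an eye field may exist.
- *That deaths are lost.* Protocol 7.1 collects them, and Protocol 9.5.2 summarises them separately. The SAP simply does not carry this through.
- *That a known dilution of the risk ratio follows.* Any figure would need injection counts for each arm and for fellow eyes, and the documents give none. Fewer injections under wait and extend is a hope of the design: Protocol 3.1 gives both arms the same retreatment criteria, and Protocol 1.1 reports fewer visits, not fewer injections, in the earlier AMD study.

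It can also be argued that study treatment includes the injection, since the schedule labels that row as injections. That reading is possible, but the glossary and Protocol 7.2 point to the drug. Different investigators could answer the item differently.

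The other outputs do not close the gap. Examination tables report findings, not adverse events, and SAP 6.10 states neither the eye nor the timing relative to injection for pressure.

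**Conclusion.** The point holds as a mismatch between the SAP and the protocol, and as an omission in the safety tables. Followed literally, SAP 6.15.1 has no category for three of six collected outcomes or for the life-threatening grade, and it leaves out the treatment arm that Protocol 9.5.2 requires. No by-arm summary of study-eye or procedure-related events is planned, and fellow-eye recording is unclear.

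The category and arm findings rest on the text alone. The causality finding assumes that investigators follow the glossary's definition of study treatment. The eye finding assumes that no unseen CRF field or table shell already deals with it. No size can be put on any bias between arms. With 43 to 52 patients per arm, the gain from the fix is clearer description rather than a more powerful test.

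**What to change.** In SAP 6.15.1:

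- Use the Protocol 7.1 grade and outcome categories unchanged.
- Tabulate adverse events by arm as n and %, split into study-eye ocular, fellow-eye ocular and non-ocular events.
- Report study-eye procedure-related events per study-eye injection in each arm, and extend SAP 6.14.3 so that injection counts are summarised in both arms.

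On the adverse-event page and in Protocol 7.1:

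- Add the affected eye, if it is not already there, and a second causality item for relation to the injection procedure.
- If the CRF cannot change, list the MedDRA terms to be treated as procedure-related before the data are analysed. This is second best, because the investigator's judgement cannot be reliably recovered later if it was never asked for.

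Reconcile the Protocol 5.5.8 statement on fellow-eye data with the recording of all adverse events in Protocol 7.1, and state which fellow-eye events are recorded.

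The cost is a small CRF revision (at most two fields) and some extra table shells. Restoring the categories and adding the arm needs no new data.
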